#### WAE Medical personnel will not do the following.

- Practice medicine
- Provide medical diagnosis or treatment to subjects
- Make suggestions or offer opinions regarding the manner in which the Investigator or site staff performs or should not perform any particular aspect of the study procedure, other than ensuring that the device is being used appropriately and safely
- Discuss a subject's condition or treatment with a subject without the approval and presence of the Investigator
- Independently collect critical study data (defined as primary or secondary endpoint data)
- Enter data in EDC systems or on paper CRFs

#### 14.5. Insurance

Where required by local/country regulation, proof and type of insurance coverage, by WAE Medical for subjects in the study will be obtained.

## **15. Monitoring**

On site and/or remote monitoring will be performed during the study to assess continued compliance with the protocol and applicable regulations. In addition, the clinical research monitor verifies that study records are adequately maintained, that data are reported in a satisfactory manner with respect to timeliness, adequacy, and accuracy, and that the Principal

Investigator continues to have sufficient staff and facilities to conduct the study safely and effectively. The Principal Investigator /institution guarantees direct access to original source documents by WAE Medical personnel, their designees, and appropriate regulatory authorities. The frequency of monitoring visits will be determined by the Sponsor. The Sponsor will contact a clinical site ahead of time to schedule monitoring visits on a date agreeable to both parties.

The study may also be subject to a quality assurance audit by WAE Medical or its designees, as well as inspection by appropriate regulatory authorities. Notice regarding audit dates/scheduling will be provided to a site ahead of time. It is important that the Principal Investigator and relevant study personnel be available during on-site monitoring visits or audits and that sufficient time is devoted to the process.

## 16. Potential Risks and Benefits

#### 16.1. Risks Associated with the Poseidon Device

Use of the PoseidonTM System during water-aided endoscopy procedures poses no new risks to the patient than the risks of the colorectal intubation. Risks associated with the Poseidon device or procedure include but are not limited to:

- Anal canal Irritation
- Tissue abrasion from cuff over inflation

In addition to the risks listed above, the risks related to endoscopy and anesthesia should be explained to the subject.

Risks related to anesthesia include:

- Postoperative confusion
- Heart attack
- Pneumonia
- Stroke

#### 16.2. Risk Minimization Actions

All efforts will be made to minimize these potential risks by:

- Selection of qualified Investigators and qualified investigational centers;
- Training the Investigators on proper technique for the Poseidon Device;
- Training the Investigators and on adherence to the study protocol and system IFU;
- Observation of procedures by the WAE Medical, Inc. and/or clinical personnel, as needed;

- Defining clear inclusion/exclusion criteria that ensure only appropriate subjects are enrolled and treated;
- Scheduled monitoring visits to the investigational site; and
- Regular communication with Investigator(s) and staff.

#### 16.3. Anticipated Benefits

Benefits of undergoing water aided endoscopy with the Poseidon device as compared to without may include:

- Potentially improved waste fluid management during water aided procedures
- Potentially less procedural time associated with improving colonoscope control
- Potentially lower risk for transmission of communicable bacteria/viruses

# 17. Safety Reporting

#### 17.1. Adverse Event Definitions

Adverse Event (AE): Any untoward medical occurrence, unintended disease or injury, or any untoward clinical signs (including an abnormal laboratory finding) in subjects, users or other persons, whether or not related to the investigational medical device.

- > **NOTE 1:** This includes events related to the investigational medical device.
- > NOTE 2: This definition includes events related to the procedures involved.
- NOTE 3: For users or other persons, this definition is restricted to events related to the investigational medical device.
- Serious Adverse Event (SAE): An adverse event that meets one or more of the following criteria:
  - o led to death,
  - o led to serious deterioration in the health of the subject, that either resulted in
    - a life-threatening illness or injury, or
    - a permanent impairment of a body structure or a body function, or
    - in-patient or prolonged hospitalization, or
    - medical or surgical intervention to prevent life-threatening illness or injury or permanent impairment to a body structure or a body function,
  - led to fetal distress, fetal death or a congenital abnormality or birth defect
  - NOTE 1: Planned hospitalization for a pre-existing condition, or a procedure required by the clinical investigational plan, without a serious deterioration in health, is not considered a serious adverse event.
- Unanticipated Adverse Device Effect (UADE): Any serious adverse event caused by, or associated with, a device, if that effect, problem, or death was not previously identified in nature, severity, or degree of incidence in the investigational plan or application (including a supplementary plan or application), or any other unanticipated serious problem associated with a device that relates to the rights, safety, or welfare of subjects.

- **Device Deficiency:** An inadequacy of an investigational medical device related to its identity, quality, durability, reliability, safety, or performance. This may include malfunctions, use error, or inadequacy in the information supplied by the manufacturer.
  - NOTE 1: Any device deficiency that might have led to a serious adverse event if a) suitable action had not been taken or b) intervention had not been made or c) if circumstances had been less fortunate is considered a reportable event.

#### 17.2. Adverse Event Relationship Definitions

All adverse events must be assessed for relationship to the study or control device (as applicable) and procedure by the Investigator. Relationship definitions are as provided below:

- Not Related: The event is due to an underlying or concurrent illness or effect of another device, drug or intervention and is not related to the investigational device, procedure or general surgery.
- **Possible:** The event has a strong temporal relationship to the use of the investigational device, procedure or general surgery, and an alternative etiology is equally or less likely.
- **Probable:** The event has a strong temporal relationship to the use of the investigational device, procedure or general surgery and another etiology is unlikely or significantly less likely.
- **Definite:** An event that can only be attributed to the use of the investigational device, procedure or general surgery.
- Not Assessable: The event's relationship to the use of the investigational device, procedure or general surgery cannot be assessed.
  - NOTE 1: Adverse events with a definite or probable relationship to the device or procedure are considered "related" events.

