#### 9.1.2. Secondary Endpoints

The secondary endpoints for this study are as follows:

- 1. Safety defined as the occurrence of all adverse events measured from the Index Procedure through the 2 Week Post Procedure Follow-up Visit.
  - a. The occurrence of > 2 device-related serious adverse events (SAE) is considered a failure 15 subjects and 1 failure in the second 15 subjects (if applicable).
- 2. Procedure time measured in minutes from the point of scope insertion to the point of scope removal (scope-in / scope-out).
- 3. Device deficiencies defined as an inadequacy of a medical device with respect to its identity, quality, durability, reliability, safety or performance including malfunctions, use errors, and inadequate labelling.

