#### 9.4. Data Analyses

To assess whether the Primary Endpoint is met in each group of 15 subjects (as applicable), Criteria A-E must all pass receive a passing score. The questionnaire attached in Appendix A will be answer during each case to document performance of the Poseidon System relative to Criteria A-E

As defined above, criterion A will be assessed on a pass/fail basis. Only 1 failure in each group of 15 will be allowed; >1 failure will result in failure of criterion A.

Criteria B – E will be assessed using a Likert-scale. After 15 each criterion has been assessed in all subjects, scores will be compiled by calculating a mean Likert-score. To pass, each criterion must have a mean Likert score of >3. A score  $\leq$  3 is considered a failure. The rating of the Likert scale will be as follows:

- A value of 1 = Strongly Disagree
- A value of 2 = Disagree
- A value of 3 = Neutral
- A value of 4 =Agree
- A value of 5 = Strongly Agree

Secondary Endpoints will be analyzed as follows:

- 1. Safety: All adverse events will be collected and assessed for relationship to the study device and/or study procedure, seriousness, and severity. Adverse events will be grouped by type and presented in frequencies. If >2 device related SAEs occur, the endpoint will fail.
- 2. Overall Procedure Time: The mean of all procedure times will be taken. There are no pass/fail criteria for this endpoint.
- 3. Device Deficiencies: All device deficiencies will be collected, grouped by type, relationship to adverse events, and presented in frequencies. There are no pass/fail criteria for this endpoint.

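### The causality levels in Section 17.2 share an undefined timing test and overlap, so a device-caused SAE may go uncounted in the safety pass/fail rule

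*Combined protocol and SAP*

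**What the plan says.** Section 17.2 has the investigator grade every adverse event on a five-level scale.

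- Possible needs a "strong temporal relationship to the use of the investigational device, procedure or general surgery, and an alternative etiology is equally or less likely".
- An event is Probable when "The event has a strong temporal relationship to the use of the investigational device, procedure or general surgery and another etiology is unlikely"; a significantly less likely alternative also suffices.
- Definite is "An event that can only be attributed to the use of the investigational device, procedure or general surgery". It has no timing condition.
- Not Related asserts that something else produced the event.
- Not Assessable is for a relationship that cannot be judged. It has no timing condition either.

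NOTE 1 then draws the line: "Adverse events with a definite or probable relationship to the device or procedure are considered" related. Possible and Not Assessable fall on the other side of it.

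That line feeds a decision. Section 9.1.2 gives Secondary Endpoint 1 as "Safety defined as the occurrence of all adverse events measured from the Index Procedure through the 2 Week Post Procedure Follow-up Visit", and Section 9.4 sets the rule: "If >2 device related SAEs occur, the endpoint will fail". Under Section 9.5 a group of 15 passes validation only if this endpoint and the Primary Endpoint both pass. Section 9.1.2 also carries a clause on the second group whose meaning is unclear, so the working below uses the rule in Section 9.4.

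**The concern.** The device is placed just before the colonoscopy and used during it, yet events are collected for two weeks. The plan therefore expects some delayed events, but it grades them on a scale whose two middle levels depend on a timing test with no definition. Separately, the middle levels overlap, although NOTE 1 treats them differently.

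With a threshold this low in a group of 15, one grading choice can settle whether the device passes. The investigator does the grading. The protocol describes no independent adjudication: a clinical events committee and a data safety monitoring board appear only in the abbreviations list (Section 21). An event that drops out through the timing test, or is coded Possible when Probable also fits, moves the result towards passing.

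**Working it through.** The plan states no event rate, power or error rate for this rule, so there is no figure of its own to reproduce. The check is mainly a reading of the levels; the arithmetic only shows scale.

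**Step 1. The levels side by side (Section 17.2 and NOTE 1).**

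| Level | Strong link in time required? | Condition on cause | Counts as related? |
|---|---|---|---|
| Not Related | No | Another cause produced it | No |
| Possible | Yes | Alternative equally or less likely | No |
| Probable | Yes | Alternative unlikely or significantly less likely | Yes |
| Definite | No | No other attribution possible | Yes |
| Not Assessable | No | Cannot be judged | No |

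**Step 2. A delayed SAE that is likely device-caused.** Suppose the investigator judges the timing plausible but not strong. Possible and Probable are then both closed. Definite is closed if any other cause is conceivable. Not Related and Not Assessable remain. Neither describes the event well, and neither counts. For the pass/fail rule only the loss of Probable matters, because Possible does not count anyway.

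**Step 3. The overlap.** Take an SAE with strong timing and an alternative cause that is significantly less likely. It meets Probable. Significantly less likely is also less likely, so it meets Possible too. No tie-break is given. Two investigators can code it differently, both within the rules, and only one coding counts.

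**Step 4. The threshold.** The endpoint fails at 3 or more. With exactly three true device SAEs and one graded outside Definite and Probable, the count is 3 − 1 = 2, which is not above 2, so the endpoint passes.

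**Step 5. Illustration of size.** Inputs: n = 15 per group (Section 5.1) and failure at 3 or more (Section 9.4). Two inputs are assumptions with no source in the documents: p, the true share of subjects with a device-related SAE (one per subject, independent), and m, the share of those SAEs graded outside Definite and Probable.

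P(fail) = P(X ≥ 3), with X ~ Binomial(15, p(1 − m)).

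- p = 5%, m = 0: the probabilities of 0, 1 and 2 events are 0.463, 0.366 and 0.135. 1 − 0.964 = 0.036.
- p = 5%, m = 50%, so rate 2.5%: 0.684, 0.263 and 0.047. 1 − 0.994 = 0.006.

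| Assumed p | m = 0 | m = 25% | m = 50% |
|---|---|---|---|
| 5% | 3.6% | 1.7% | 0.6% |
| 10% | 18.4% | 9.7% | 3.6% |
| 20% | 60.2% | 39.6% | 18.4% |
| 30% | 87.3% | 69.0% | 39.6% |

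Given exactly three true device SAEs, the endpoint fails only if all three are counted, with probability (1 − m)³. That is 0.9³ = 0.729, 0.75³ = 0.422 and 0.5³ = 0.125 for m of 10%, 25% and 50%. This treats the gradings as independent, which is doubtful with one or two sites.

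**The case against.** The strongest reply is that Section 17.2 contains no time limit. A reader might infer that most of the two-week window can reach the rule only through Definite. The documents do not support that: they nowhere say that onset some days after the procedure cannot be strongly linked in time, and an investigator may grade an anal-canal injury found on day 5 as Probable, in which case it counts. This stands, and it limits the point to a loss that may happen. It does not remove it, because an undefined term lets another investigator decide the opposite.

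A reader might also infer that the scale has no place at all for such an event. Not Assessable is a residual level, and a late event with no other possible cause is Definite and counts. What stands is poor fit: an event judged likely device-caused has been assessed, and putting it under Not Assessable removes it from the count.

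Nor does the lack of a level for events with a more likely alternative cause weaken the pass/fail rule. Such events should not count as related, so a further level would change the tabulation only.

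Finally, safety visibility is kept. All SAEs go to the sponsor within 3 calendar days whatever the grade (Section 17.4), adverse events are tabulated (Section 9.4), and the sponsor may stop for safety (Section 18.1). That also stands. The loss is confined to the count that decides validation.

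**Conclusion.** The concern holds as a wording defect behind a pass/fail decision. Two faults are established from the text alone: Possible and Probable share a necessary timing condition that is never defined, and they overlap with no tie-break although NOTE 1 puts them on opposite sides of the related line. The overlap needs no assumption about late events.

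The consequence is possible, not certain. It matters when the true count is at or just above three. How often that happens depends on a device-related SAE rate that the documents do not give. The study is classed as non-significant risk (Section 5.3), and the device risks listed are irritation and abrasion (Section 16.1). At an assumed 5% risk the absolute change is at most about 3 percentage points even if half the events are lost (3.6% to 0.6%). A reader might take the larger differences at 20% or 30% as the expected effect, but no passage supports such rates or any particular share of lost events. The change should be made because it is cheap and the rule decides validation, not because a large effect has been shown.

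**What to change.** Amend Section 17.2, preferably before any SAE is graded, so that the change is not made with results in view.

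1. In both Possible and Probable, ask for a plausible instead of a strong temporal relationship, and state that onset at any time through the 2-week visit can qualify. The added statement is needed because plausible alone would be as open as strong.
2. Keep the present wording on alternative causes, but require the highest level whose definition is met, so that an event meeting both Possible and Probable is coded Probable. Keeping that wording leaves no gap for an alternative that is only modestly less likely.
3. In Section 9.4, report the Secondary Endpoint 1 result a second time, counting Possible and Not Assessable device SAEs as related, so that readers can see whether the pass depends on grading.

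The cost is a few lines of text, matching instructions on the adverse event form and one extra line in the report. Sample size and visits do not change. The downside is that slightly more late events may be rated related, which makes the endpoint slightly harder to pass.

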#### 17.3. Adverse Event Severity Definitions

All adverse events must be assessed for severity by the Investigator. Severity definitions are as provided below:

- Mild: Awareness of signs or symptoms, but easily tolerated; are of minor irritant type; causing no loss of time from normal activities; symptoms would not require medication or a medical evaluation; signs or symptoms are transient.
- **Moderate:** Interferes with the subject's usual activity and/or requires symptomatic treatment.
- Severe: Symptom(s) causing severe discomfort and significant impact of the subject's usual activity and requires treatment

#### 17.4. Investigator Reportable Events and Timelines

As part of this study all AEs, regardless of relationship to the device and/or procedure, will be captured on the applicable CRF and reported to the Sponsor. Event types and associated reporting timelines are listed below:

- All AEs regardless of the relationship to the device and/or procedure must be reported to the Sponsor within **10 business days** of first becoming aware.
- All SAEs regardless of relationship to the device and/or procedure must be reported to the Sponsor within **3 calendar days** of first becoming aware.
- All Device Deficiencies must be reported to the Sponsor withing **3 calendar days** of first becoming aware.
- All UADEs must be reported to the Sponsor within 1 business day of first becoming aware of the event.

"Becoming aware" is the point at which a member of the study team has acquired information that reasonably suggests that a reportable AE has occurred. Adverse Event reporting for this study will begin at the point of the Index Procedure and will extend through end of study for each individual subject. Underlying diseases and pre-existing conditions are not considered AEs.

NOTE 1: Intraprocedural bleeding that occurs during a procedure with the study or control device that can be managed endoscopically during the procedure is not considered an AE.

Reporting an AE or Device Deficiency to the Sponsor within the timeframes noted above can be done by submitting the Adverse Event or Device Deficiency CRF in the EDC system with as much event data as possible, by emailing the Sponsor, or by calling the Sponsor. For AEs, the medical diagnosis should be reported as the Event Term on the CRF instead of individual symptoms. Each individual AE or Device Deficiency should be reported on its own Adverse Event CRF.

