#### 6.2. Exclusion Criteria

- 1. Subject unable or unwilling to provide informed consent.
- 2. Subjects with prolapsing hemorrhoids that require intervention or hemorrhoids that have been treated within last 3 months.
- 3. Prior TAMIS (Trans anal minimally invasive surgery) or TEMS (Trans anal micro endoscopic surgery).
- 4. Any condition that in the opinion of the Investigator would create an unsafe clinical situation that would not allow the patient to safely undergo an endoscopic procedure.
- 5. Pregnant or lactating women or women of childbearing potential who do not employ a reliable method of contraception as judged by the Investigator, and/or are not willing to use reliable contraception for the duration of study participation.
- 6. Patient is enrolled in another trial that could interfere with the endpoint analyses of this trial.

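### Section 17.4 says pre-existing conditions are not AEs and gives no worsening clause, at odds with 17.1 and 17.2, so device-aggravated anorectal disease could go unrecorded.

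*Combined protocol and SAP*

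**What the plan says.** **Definition.** Section 17.1 defines an AE as "Any untoward medical occurrence, unintended disease or injury, or any untoward clinical signs", related to the device or not. Its notes bring in events related to the device and to the procedures. An SAE is an AE that also meets a seriousness criterion, one of which is that it "led to serious deterioration in the health of the subject" with specified outcomes. The SAE note excludes "Planned hospitalization for a pre-existing condition, or a procedure required by the clinical investigational plan, without a serious deterioration in health".

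**Reporting.** Section 17.4 starts AE reporting at the index procedure and continues: "Underlying diseases and pre-existing conditions are not considered AEs". Later it tells sites to enter the medical diagnosis as the Event Term rather than individual symptoms.

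**Relationship.** Section 17.2 has a Not Related category for events due to underlying or concurrent illness. Only probable or definite events count as related.

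**Endpoint.** Section 9.1.2 gives Secondary Endpoint 1 as "Safety defined as the occurrence of all adverse events measured from the Index Procedure through the 2 Week Post Procedure Follow-up Visit". Section 9.4 tabulates AE frequencies by type and adds the pass/fail rule: "If >2 device related SAEs occur, the endpoint will fail". Section 9.5 makes this endpoint, with the Primary Endpoint, a condition for passing validation.

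**Population and risk.** Section 6.2 excludes "Subjects with prolapsing hemorrhoids that require intervention or hemorrhoids that have been treated within last 3 months", and prior TAMIS or TEMS. Section 16.1 names anal canal irritation and "Tissue abrasion from cuff over inflation" as device risks.

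**The concern.** The device is an introducer placed in the anal canal and held by an inflated balloon. Eligibility rules out only some hemorrhoid disease and two types of prior surgery. Apart from the investigator's general safety judgement (exclusion criterion 4), subjects with other hemorrhoids or anorectal disease can enrol. Aggravation of such disease is a foreseeable local harm and one that a first clinical study of the device should capture.

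Section 17.4 is where a site looks to decide what to report, and it does narrow 17.1 elsewhere: its own note removes intraprocedural bleeding that is managed endoscopically. A coordinator could reasonably treat the sentence on pre-existing conditions as another exclusion. Two sites, or two investigators, could then handle the same event differently. At stake is the completeness of the AE table and, more remotely, the SAE count that feeds the validation decision.

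**Working it through.** The plan gives no SAE rate, alpha or power, so there is no figure to reproduce. The check is mainly of the text.

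**Step 1: follow one event through the plan.** Take a subject with known, untreated, non-prolapsing hemorrhoids that flare after the procedure.

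| Section | Treatment of the flare |
|---|---|
| 6.2 | Subject is eligible, unless criterion 4 is invoked |
| 17.1, AE definition | An untoward occurrence after device use: an AE |
| 17.1, SAE note | Silent unless hospitalization is involved; implies that serious deterioration of a prior condition counts |
| 17.2 | Even if due to underlying illness, it has a relationship category, which presupposes that it was recorded |
| 17.4, pre-existing conditions | Literally, not an AE |
| 17.4, Event Term | Entered under its diagnosis, hemorrhoids, which the subject already had |

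Sections 17.1 and 17.2 record the event first and attribute it afterwards. Section 17.4, read literally, removes it before seriousness or relationship is assessed. The Event Term instruction strengthens that reading, because the term entered is the pre-existing diagnosis.

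**Step 2: is there a baseline?** Table 1 schedules Medical History at the index procedure. The data list in 8.4.2 omits it, as does the index visit list in the synopsis. The information needed to separate worsening from an unchanged condition is therefore not firmly specified.

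**Step 3: effect on the AE table.** With 15 subjects per group, one subject's event left out lowers the proportion of subjects with that event by 1/15 = 6.7 percentage points.

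**Step 4: effect on pass/fail.** A non-serious worsening has no effect, since only device-related SAEs count. A serious one matters only if it is also judged probably or definitely related. Under 9.4 the endpoint fails at 3, so one missing event changes the result only when the true count is exactly 3 (3 − 1 = 2, a pass).

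**Step 5: what loss of SAEs would do, on assumed values.** Let p be the true device-related SAE rate per subject (at most one each) and f the share not recorded. Neither is in the documents. The chance that a group of 15 fails is P(X ≥ 3), with X binomial(15, p(1 − f)). For p = 10% and f = 0:

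1 − 0.9^15 − 15(0.1)(0.9^14) − 105(0.1²)(0.9^13) = 1 − 0.2059 − 0.3432 − 0.2669 = 0.184 (from unrounded terms).

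| p | f = 0 | f = 25% | f = 50% |
|---|---|---|---|
| 5% | 0.036 | 0.017 | 0.006 |
| 10% | 0.184 | 0.097 | 0.036 |
| 20% | 0.602 | 0.396 | 0.184 |
| 30% | 0.873 | 0.690 | 0.396 |

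The table shows only that the rule is sensitive to lost SAEs. It does not show that SAEs would be lost: nothing in the plan suggests that f is near 25% or 50% for serious events. It uses the threshold in 9.4; the wording in 9.1.2 leaves the threshold for the second group unclear.

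**The case against.** The best defence is that the sentence means only that baseline conditions are not logged as events. It directly follows the statement of when reporting starts, it does not mention worsening, and a deterioration after the procedure is a new occurrence rather than a pre-existing condition. The broad AE definition, the serious-deterioration criterion, the SAE note and the Not Related category all point towards recording. The named risks, irritation and abrasion, are new injuries and are AEs even in a subject with hemorrhoids.

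Much of this stands. It shows that the likely intention is to record worsening, and that the loss is possible rather than certain. It does not remove the conflict. No text says that worsening is an AE, the SAE note covers only planned hospitalization, and the Event Term instruction gives a literal reader a direct route to leaving the event out.

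A reader might infer something stronger: that aggravated anorectal disease would drop out of the endpoint that decides validation, tilting that decision towards a pass. The documents do not support this. Several provisions favour recording, non-serious worsening cannot alter pass/fail, and no rate is given from which a distortion of the SAE count could be estimated.

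**Conclusion.** The point holds as an inconsistency between 17.4 and 17.1 and 17.2, with a missing worsening clause. Device-aggravated hemorrhoids or other anorectal disease could go unrecorded if a site follows 17.4 to the letter. The main consequence is understated AE frequencies in Secondary Endpoint 1, at 6.7 percentage points per affected subject in a group of 15. The validation decision is touched only if the unrecorded worsening is a device-related SAE and its loss takes the count from above 2 to 2 or fewer, which is the less likely case.

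This rests on a literal reading of 17.4 that is available to sites but not compelled, and on some enrolled subjects having anorectal disease, which 6.2 permits. The binomial figures rest on assumed rates, and the conclusion does not depend on them.

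**What to change.** 1. Reconcile 17.4 with 17.1 and 17.2, for example: underlying diseases and conditions present before the index procedure are not AEs unless they worsen in severity, frequency or character on or after the index procedure; any such worsening is recorded as an AE and assessed for seriousness and relationship. Repeat this in the CRF guidance, and say there that the Event Term should identify the event as a worsening.
2. Add Medical History, including anorectal history, to the index-visit data list in 8.4.2 so that it matches Table 1, and to the synopsis list. This supplies the baseline against which worsening is judged.

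The cost is one sentence in 17.4, one item in each data list, and the matching CRF field and guidance. Slightly more AEs will be recorded. Neither the sample size nor the pass/fail rule changes.
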